1.1 Synopsis

Protocol Title: A Randomized, Multi-Center, Double Blinded, Self-Initiated, Single Treatment Study Comparing Sitavig® (acyclovir) 50 mg Muco-adhesive Buccal Tablet to Placebo in the Treatment of Herpes Labialis in Immunocompetent Adults

Objectives and Endpoints:

| Objectives | Endpoints |
|--|--|
| Primary | |
| To compare duration of episode (DOE) of cold sores between Sitavig and placebo in participants experiencing a recurrence of herpes labialis (HL). | Duration of episode (DOE) will be measured in hours (using the Science 37 Platform), of a single treated HL lesion. Observation period to determine healing will last up to 14 days (DurEp14). |
| | Duration of episode (DOE) is defined as the time from the initiation of treatment (study intervention initiation) to the healing of primary lesions (loss of crust) for participants who experience a vesicular lesion. For participants whose primary lesions are not vesicular in nature, duration of episode is the time from study intervention initiation to the return to normal skin as determined by the independent blinded reader of the participant's face images using a 6-point Likert scale or to the cessation of symptoms, whichever comes last. |

Version 5.0 Page: 15 of 68

| Objectives | Endpoints |
|--|--|
| Secondary | |
| To compare the incidence of aborted lesions between participants receiving Sitavig and placebo after experiencing prodromal symptoms of a recurrence of HL. To compare the incidence of recurrence of primary HL lesions between participants | Incidence of aborted lesions, defined as treated HL lesions that do not progress to the vesicular stage. A lesion that returns to normal skin without forming a vesicle or crust will be counted as an aborted lesion. Observation period to determine healing will last up to 14 days (Abort14). |
| receiving Sitavig and placebo during a 12- month follow-up period. | Incidence of recurrence of HL lesions during the 12-month follow-up period (IncRec12). |
| To compare the time to recurrence of primary HL lesions between participants receiving Sitavig and placebo during a 12-month follow-up period. To assess safety and tolerability of the investigational products. | Recurrence is determined by assessment from the investigator and documented using numerical rating scale (NRS) symptom scores and face images using the Science 37 Platform. |

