This is a 14-day clinical trial (Treatment Phase) to test the hypothesis that Sitavig (acyclovir) buccal tablet safely and effectively reduces duration of a herpes labialis cold sore of the lip in immunocompetent adults. Eligible participants who pass screening procedures will be randomized and moved into the Run-in Phase. Participants will be randomly assigned one of two treatment groups - Sitavig (acyclovir) 50 mg buccal tablets or a placebo buccal tablet. The randomization assignment is such that there is a 1 in 2 chance of receiving the placebo treatment. Participants will have a 6 month eligibility window in which they can self-initiate treatment should prodromal symptoms start. At the start of prodromal symptoms, participants will self-

Version 5.0

Page: 17 of 68

initiate treatment and record face images as well as symptom scores over the next 14 days. Treatment consists of a single application (of the buccal tablet) beginning on Day 1. Face images and symptom scores are captured over the 14 day Treatment Phase.

Study Duration (Treatment Phase): 14 days

Study Duration (Follow up Phase): 12 months

Investigational Medicinal Product (IMP): Sitavig (acyclovir) 50 mg buccal tablet or placebo buccal tablet

Treatment Duration: 1 day

Visit Frequency: After the start of treatment, two visits within the 14 day Treatment Phase. Additional follow up by phone will occur at 3, 6, 9 and 12 months after treatment.

Condition/Disease: Herpes labialis of the lips caused by herpes simplex virus type 1 (HSV-1) or herpes simplex virus type 2 (HSV-2).

Study Hypothesis: Sitavig (acyclovir) buccal tablet effectively reduces the duration of a cold sore of the lips.

Health Measurement/Observation: Independent blinded lesion evaluation using a 6-point Likert scale and 0-10 NRS symptom scores will occur pre and post treatment.

Intervention Groups: Participants will be randomized in 1:1 fashion (active or placebo) with a single dose of study intervention.

Data Monitoring/Other Committee: No

Version 5.0 Page: 18 of 68

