The demographic characteristics were similar between treatment and placebo group. All patients in both groups experienced at least 4 episodes of herpes labials in the last 12 months and more than 2/3 had at least 5 episodes per year.

The results of the study showed that time to healing of primary lesion was significantly reduced (p=0.0150) in the ABT 50 mg group compared to the placebo group. The clinical reduction was 0.57 days. The secondary objectives were all improved compared to the placebo group. More patients had aborted lesions, and the duration of non-primary vesicular lesions was reduced. Data showed that ABT 50 mg reduces the occurrence of the vesicular lesions. The duration of the herpes episode and the duration and severity of symptoms were all reduced by the treatment. A notable result in this study was that there were significantly fewer patients in the treatment group who had recurrences of primary lesions than in the placebo group. The difference was even greater in patients who inserted ABT 50 mg correctly within 1 hour of symptoms.

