9.1 Statistical Hypotheses

The primary efficacy endpoint is the duration of episode (DOE). The treatment comparison between Sitavig and placebo will be made as 2-sided at the significance level of 0.05. No multiplicity adjustment will be made.

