9.4.2 Primary Endpoint

The primary efficacy variable is:

• Duration of episode (DOE) will be measured in hours (using the Science 37 Platform), of a single treated HL lesion. Observation period to determine healing will last up to 14 days (DurEp14).

Duration of episode (DOE) is defined as the time from the initiation of treatment (study intervention) to the healing of primary lesions (loss of crust) for participants who experience a vesicular lesion. For participants whose primary lesions are not vesicular in nature, duration of episode is the time from study intervention initiation to the return to normal skin as determined by the independent blinded reader of the participant's face images using a 6-point Likert scale or the cessation of symptoms, whichever comes last. For the subjects who do not demonstrate the healing of primary lesions or cessation of symptoms, the data will be censored at 14 days (14*24 hours) or time of loss of follow-up, whichever happens earlier.

Duration of episode (DOE) will be estimated and plotted using Kaplan-Meier method and analyzed using log-rank test.

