7.7 Efficacy Analysis

7.7.1 Analysis of Primary Efficacy Endpoint

The primary efficacy variable is DOE, which will be measured in hours (using the Science 37 Platform), of a single treated HL lesion. Observation period to determine healing will last up to 14 days. DOE is defined in detail in section 4.

DOE will be analyzed using Kaplan-Meier method for treatment groups (Sitavig and Placebo). Median, associated 95% CIs and survival probabilities will be estimated using Kaplan-Meier (KM) Method. DOE curves between the two treatment groups will be compared with a log-rank test and the corresponding hazard ratio (with 95% CI) will be estimated using Cox proportional hazard method.

The analysis of primary efficacy endpoint will be performed on both ITT and PP population, with PP population being the primary efficacy population and ITT population being secondary. Individual subject data for DOE will be presented in Listing.

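### The primary analysis of episode duration plans no between-arm difference in hours with a confidence interval, although the hypothesis is a reduction in duration

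*Protocol*

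**What the plan says.** The synopsis (Protocol 1.1) sets the question on the time scale: "Study Hypothesis: Sitavig (acyclovir) buccal tablet effectively reduces the duration of a cold sore of the lips". The endpoint is on the same scale: "Duration of episode (DOE) will be measured in hours (using the Science 37 Platform), of a single treated HL lesion".

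Protocol 9.4.2 gives the analysis and names no effect estimate: "Duration of episode (DOE) will be estimated and plotted using Kaplan-Meier method and analyzed using log-rank test". Protocol 9.1 fixes a two-sided test at 0.05.

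SAP 7.7.1 adds two things. The first is a summary within each arm: "Median, associated 95% CIs and survival probabilities will be estimated using Kaplan-Meier (KM) Method". The second is a comparison between arms: "the corresponding hazard ratio (with 95% CI) will be estimated using Cox proportional hazard method". The hazard ratio is the only between-arm estimate planned for DOE. Neither document plans a difference in medians, a difference in restricted means or a time ratio, and SAP 7.13 (changes from the protocol) adds nothing here. SAP 7.7.3 carries the same method over to DOE by time of treatment start and to time to cessation of symptoms.

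**The concern.** A reader of the results will ask how many hours shorter the cold sore was, and how sure we are. As planned, the report will answer with two medians, each with its own interval, a p-value and a hazard ratio. Two separate intervals for the medians are not an interval for their difference. The hazard ratio has an interval, but on a scale that does not convert to hours without further assumptions.

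Constancy of the ratio is also doubtful. DOE ends at loss of crust for vesicular lesions. For the others it ends at normal skin or the end of symptoms, whichever is later (SAP section 4). Protocol 2.2 reports that the earlier trial saw both faster healing and more aborted lesions. A treatment acting on such a mixture need not give a constant ratio. At stake is the estimate of benefit, not the validity of the test.

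**Working it through.** The sample-size sections are redacted or not visible, so there is no planned effect to reproduce. All distributions below are assumptions.

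**1. A hazard ratio does not fix the hours saved, even under proportional hazards.** Take Weibull healing times with placebo median m and shape k, and a healing ratio HR above 1 favouring the tablet. Then

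median reduction = m × (1 − HR^(−1/k)).

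With m = 120, 168 or 216 h, k = 1.0, 1.5 or 2.5, and HR = 1.2:
- smallest: 120 × (1 − 1.2^(−0.4)) = 120 × 0.0703 = 8.4 h
- largest: 216 × (1 − 1/1.2) = 36.0 h

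The restricted mean reduction is the integral of the difference between the survival curves from 0 to 336 h.

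| HR | Median reduction (h) | Restricted mean reduction to 336 h (h) |
|---|---|---|
| 1.2 | 8.4 to 36.0 | 8.7 to 18.1 |
| 1.3 | 12.0 to 49.8 | 12.3 to 26.1 |

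**2. Mixture of episode types.** Simulated gamma mixtures, 20,000 per arm, horizon 306 h. On placebo, 30% of lesions abort (mean 72 h, SD 40) and the rest are vesicular (mean 190 h, SD 40, 60 or 90). The tablet either shortens vesicular episodes by 20 h, with the SD scaled in proportion, or raises the aborted share to 42%. The restricted mean saving was 12.0 to 14.3 h throughout, while the Cox ratio ran from 1.13 to 1.43. With more aborted lesions, the ratio was 1.30 to 1.43 before 96 h and 0.99 to 1.02 after 192 h. With shorter vesicular episodes it was 1.01 to 1.12 before 96 h and higher later; the late values depend on how the shift is modelled.

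Mechanism is not the only driver. In a variant with separately simulated savings of 11.5 to 13.9 h, the Cox ratios were:

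| Vesicular SD (h) | Shorter vesicular episodes | More aborted lesions |
|---|---|---|
| 40 | 1.35 | 1.15 |
| 60 | 1.20 | 1.15 |
| 90 | 1.15 | 1.16 |

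At SD 90 the two mechanisms cannot be told apart; the assumed spread matters as well.

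**3. What an interval in hours would look like.** Weibull, m = 168 h, k = 1.5, HR = 1.2, complete follow-up to 336 h, 3,000 runs. The restricted mean interval is compared with one assembled afterwards from the two median intervals (MOVER method).

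| Per arm | Restricted mean: coverage, mean width | From median CIs: coverage, mean width |
|---|---|---|
| 100 | 0.943, 55.1 h | 0.974, 93.5 h |
| 200 | 0.950, 39.0 h | 0.967, 63.6 h |
| 350 | 0.957, 29.5 h | 0.972, 48.9 h |

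**4. Horizon.** The last image is on Day 14 at 19:00 ± 60 minutes (Protocol 8.1.5.6), and Day 1 is the dosing date (SAP 3.4).
- Dose just before midnight on Day 1: 12 × 24 + 19 − 1 = 306 h to the earliest permitted last image.
- Dose at 00:00 on Day 1: 13 × 24 + 20 = 332 h to the latest.

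No scheduled image reaches 14 × 24 = 336 h. A horizon of 300 h lies within follow-up for every completer.

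**The case against.** The plan is conventional and coherent: log-rank test, Kaplan-Meier medians and a Cox ratio. A reader might infer that the trial cannot state a reduction in hours. That goes too far. The medians are in hours, their difference can be read off, and the data would support an interval. What is missing is a prespecified one. Nor do the documents support calling the log-rank p-value invalid.

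A reader might also want to set the result against the earlier trial, of which Protocol 2.2 says: "The clinical reduction was 0.57 days". That comparison should not be made. The figure concerns healing of the primary lesion, while duration of episode was a separate secondary objective there. The protocol gives neither its interval nor whether it is a mean or a median.

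Non-proportional hazards are plausible from the endpoint definition but are not shown by the documents. The mechanism is also partly covered by the separate endpoint on aborted lesions (SAP 7.7.2).

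Finally, a restricted mean difference can disagree with the log-rank test. In one assumed setting (250 per arm, vesicular SD 60, aborted share 42% against 30%, 300 runs), its interval excluded zero while the log-rank test was non-significant in about 22% of runs. With shorter vesicular episodes instead, about 10% disagreed in the opposite direction. This stands, and it is why the added estimate must not become a second route to a positive claim.

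**Conclusion.** The gap is real but limited. The hypothesis and endpoint are about duration in hours, and the only planned between-arm estimate for DOE is a hazard ratio. As planned, the trial will not report a reduction in hours with a confidence interval.

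The size of the ambiguity can only be illustrated. A ratio of 1.2 fits median reductions from 8.4 to 36.0 h under the assumed Weibull shapes, and similar savings of about 12 to 14 h gave Cox ratios from 1.13 to 1.43 under the assumed mixtures. None of these distributions comes from the documents.

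One might conclude that the restricted mean should replace the hazard ratio as the headline result. The documents do not settle that choice, and the point does not need it. This is a cheap improvement in estimation, not a fault in the primary test.

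**What to change.** In SAP 7.7.1:

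1. Keep the log-rank test as the sole primary test, and keep the Cox ratio.
2. Add the between-arm difference in restricted mean DOE, in hours, with 95% CI, for PP and ITT. Fix the horizon before unblinding at a time that all completers reach, for example 300 h.
3. State that this is an estimate of effect size and does not alter the test decision, whichever way the two results fall.
4. Add a sensitivity analysis that censors dropouts at their last assessment. SAP section 4 censors unhealed subjects at 336 h whatever happened, and SAP 3.3 sets missing healing times to 336 h. Both rules would count such subjects as unhealed for the whole horizon. Protocol 9.4.2 already censors at loss to follow-up if that comes first. Subjects who healed at an unrecorded time could be censored at the last image showing the lesion unhealed.

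The cost is a few lines of text and a standard analysis. No new data are needed, and alpha and the primary test are unchanged. The downside is one more estimate, which may at times disagree with the log-rank result.

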1.2 Scheme

Figure 1 – Study Scheme

| Screening Randomizati Phase | | Run-in Phase | Start Study Intervention | | Treatment Phase Follow-Up Phase | | | | | | | p Phase ª | |
|--|---|---|---|--|--|---|--|---|---|---|---|---|--|
| Within 35 days the start of th Run-in Phas | e | Start 6-month eligibility window | Day 1 | Day 2 | 3 | 4-6 | Day 7 | 8-13 | Day 14 (+ 2 days) | 3 months (± 3 days) | 6 months (± 3 days) | 9 months (± 3 days) | 12 months (± 3 days) |
| Visit 1 Baseline Face image (no symptoms) Photo and e-diary/App training e-diary/App NRS symptom scores | * | Weekly virtual check-in Virtual training refresher | Pre/post treatment Face images Subject takes IMP at home e-diary/App NRS symptom scores | Visit 2 (within 24 hours of treatment start) Face image e-diary/App NRS symptom scores | Face image e-diary/App NRS symptom & QoL scores | Face image e-diary/App NRS symptom scores | Face image e-diary/App NRS symptom & QoL scores | Face image e-diary/App NRS symptom scores | Visit 3 Face image e-diary/App symptom & QoL scores Global assessment | Phone call e-diary/App Weekly virtual check-in Ad-hoc NRS symptom scores Face image | Phone call e-diary/App Weekly virtual check-in Ad-hoc NRS symptom scores Face image | Phone call e-diary/App Weekly virtual check-in Ad-hoc NRS symptom scores Face image | End of Study Phone call e-diary/App Weekly virtual check-in Ad-hoc NRS symptom scores Face image |
| # = participant randomized into one of two blinded study interventions: • Sitavig 50 mg buccal tablet • Placebo buccal tablet • participant experiences prodromal symptoms that require study intervention a follow-up dates are established from the Day 1 dosing date ** Visit 2 may occur within 36 hours of Day 1 dosing time | | | | | | | | | | | | | |

Version 5.0 Page: 19 of 68

1.3 Schedule of Activities (SoA)

| | Screening & Randomization Phase | Run-in Phase | Treatment Phase | | | Follow-Up Phase ^g | | | | | | | |
|---------------------------------|---------------------------------------|------------------------------------|-----------------|-----|----|------------------------------|----|------|----------------|-------------------------------|-------------------------------|-------------------------------|--------------------------------|
| Visit Number | 1 | | | 2 | | | | | 3 ^d | | | | |
| Day or Milestone | Within 35 days of Run-in start | Six-month eligibility window | 1 | 1-2 | 3 | 4-6 | 7 | 8-13 | 14 +2d | 3 months (call) ±3 days | 6 months (call) ±3 days | 9 months (call) ±3 days | 12 months (call) ±3 days |
| Virtual visit | X | | | X | | | | | X | | | | |
| Informed consent | X | | | | | | | | | | | | |
| Inclusion/Exclusion criteria | X | | | X | | | | | | | | | |
| Participant demographics | X | | | | | | | | | | | | |
| Medical History | X | | | | | | | | | | | | |
| Prior/Concomitant Medication | X | X | | X | | | | | X | X | X | X | X |
| History of drug and alcohol use | X | | | | | | | | | | | | |
| Urine drug screen | X | | | | | | | | | | | | |
| Urine pregnancy test | X | | Xª | | | | | | | | | | |
| BP and pulse | X | | | X | | | | | X | | | | |
| Platform (re)training | X | X | | | | | | | | | | | |
| IMP dosing instructions | X | | | | | | | | | | | | |
| NRS symptom scores | X | | Xb | Χ | X | X | X | X | X | Xe | Xe | Xe | Xe |
| Face images | X | | X^{b} | Xc | Xc | Xc | Xc | Xc | Xc | Xe | Xe | Xe | Xe |
| Randomizationf | X | | | | | | | | | | | | |
| Virtual weekly check-ins | | X | | | | | | | | X | X | X | X |
| Start of prodromal symptoms | | | X | | | | | | | | | | |
| IMP administration | | | X | | | | | | | | | | |
| IMP compliance check | | | | X | | | | | X | | | | |
| OHIP-14 | | | | | X | | X | | X | | | | |
| Global assessment | | | | | | | | | X | | | | |
| IMP kit return | | | | | | | | | X | | | | |
| Adverse events | X | X | X | X | X | X | X | X | X | X | X | X | X |
| End of Study | | | | | | | | | | | | | X |

^a The urine pregnancy test must be performed prior to the start of study intervention and be negative (not pregnant).

^b NRS symptom scores and face images can be collected at 09:00, 14:00 and 19:00 that day. Depending on the time study intervention starts, NRS symptom scores and face images may or may not be collected for Day 1.

^c Face images taken at 09:00, 14:00 and 19:00 each day.

^d The 2-day window pertains to all Visit 3 tasks except the NRS symptom scores, face images, QoL-OHIP and Global assessment which should be collected at their respective nominal times (±60 minutes) on Day 14.

^e Face image(s) and NRS symptom score(s) required if a new outbreak of herpes labialis is suspected by the investigator.

^f After successful completion of all screening procedures.

^g Follow up dates established using the Day 1 dosing date.

Version 5.0 Page: 20 of 68

2. Introduction

Herpes labialis (HL), also called cold sores of the lip, is an infection primarily caused by herpes simplex virus type 1 (HSV-1) and occasionally herpes simplex virus type 2 (HSV-2). The infection is typically spread between people by direct contact. HL is a rash of the skin and mucous membranes (in particular, the lips) and is characterized by erythema and blisters that are preceded and accompanied by tingling, itching or burning pain [1].

For an infection to manifest, the virus must come in contact with mucosal surfaces or abraded skin. The viral replication takes place at the site of primary infection (epithelial cells), either as an intact virion or the capsid is transported in a retrograde fashion by neurons to the dorsal root ganglia, where, after another round of viral replication, latency is established. After primary infection, the virus recedes via the sensory nerve into the respective ganglion (usually the trigeminal ganglion), where it lies latent throughout the individual's lifetime. Stimuli such as fever, menstruation, sunlight, and upper respiratory infections can reactivate the virus, after which it returns to the epithelial cells via the sensory nerve [2].

HSV1 and HSV2 infections rest in a dormant (inactive) state until the virus is activated. During an active phase of infection, a visible outbreak of sores may be observed. Infrequently, life-threatening infection (e.g., encephalitis) may occur. The more severe the primary infection (as reflected by the size, number, and extent of lesions) the more likely it may be that recurrences may develop when triggered [3,4].

After a period of latency, a proper stimulus may cause reactivation. Reactivation of the virus becomes evident at mucocutaneous sites, appearing as skin vesicles or mucosal ulcers. The blisters in cold sores appear as fluid filled pockets beneath the surface of the skin around the mouth or on the lips. They can break open, ooze, and crust over, lasting for around 7 to 10 days. The severity of the disease varies from person to person and the symptoms can be very painful. There are different products that are used to treat cold sores. There are prescription drugs which are very effective and there are the over the counter (OTC) products as well which can bring relief to the patients [3,4,5].

2.1 Study Rationale

2.2 Background

A randomized, double-blinded, multicentered, placebo-controlled, single-dose trial of early administration of Acyclovir 50-mg mucoadhesive buccal tablets was conducted to evaluate efficacy and safety for the treatment of herpes labialis in immunocompetent patients. This muco-adhesive buccal tablet is designed to allow the rapid and prolonged release of acyclovir in high concentrations directly into the oral cavity at the site of the infection of herpes labialis.

The primary objective of this study was to demonstrate the efficacy of a single mucoadhesive acyclovir buccal tablet (ABT) compared to a single dose of a placebo. The efficacy was measured using the time to healing of the primary vesicular lesion (time-to-event). Secondary objectives were to compare the efficacy of ABT 50 mg versus placebo on the evolution of prodromal symptoms to aborted lesions, healing of non-primary lesions, duration of episode,

[figure not shown]
Version 5.0 Page: 21 of 68

duration of symptoms, healing of the aborted primary lesions and intra oral/mucosal non primary lesions, and the incidence of and time to recurrence during 9 months following treatment. Prodromal symptoms (such as pain, tenderness, itching, tingling or discomfort) are early symptoms that herald the onset of a cold sore outbreak.

Local tolerability and general safety were studied. The concentration of acyclovir in the saliva and the adhesion time (incidence of tablets detaching and/or being swallowed within 6 hours after tablet placement) was evaluated as well. Two populations were analyzed in this protocol: the modified intent to treat (mITT) population of everyone who took at least one dose and whose lesion reached the vesicular stage and the intent to treat (ITT) population that took at least one dose of the treatment medication.

After initiating treatment, subjects were under evaluation for up to 14 days or until the primary lesions healed. Subjects were told to fill out a questionnaire and visual analogue scale each evening to record their symptoms. Patients were to return to the clinic within 36 hours of application of the tablet. Evaluation took place on days 1, 3, 5, 7, and 14 (or healing occurred). Additionally, follow-up visits were conducted every 3 months for up to 9 months for recurrence. Adverse effects were to be reported.

The demographic characteristics were similar between treatment and placebo group. All patients in both groups experienced at least 4 episodes of herpes labials in the last 12 months and more than 2/3 had at least 5 episodes per year.

The results of the study showed that time to healing of primary lesion was significantly reduced (p=0.0150) in the ABT 50 mg group compared to the placebo group. The clinical reduction was 0.57 days. The secondary objectives were all improved compared to the placebo group. More patients had aborted lesions, and the duration of non-primary vesicular lesions was reduced. Data showed that ABT 50 mg reduces the occurrence of the vesicular lesions. The duration of the herpes episode and the duration and severity of symptoms were all reduced by the treatment. A notable result in this study was that there were significantly fewer patients in the treatment group who had recurrences of primary lesions than in the placebo group. The difference was even greater in patients who inserted ABT 50 mg correctly within 1 hour of symptoms.

